This parametric comparative trial will randomly assign 140 inner-city adolescents with ADHD to (1) CASH-AA Only or (2) CASH-AA + MIP. Treatment will occur in community behavioral health clinics. All participants will receive behavioral interventions (CASH-AA): family psychoeducation in ADHD symptoms, executive functioning, and developmental impacts; family-based motivation and ADHD accommodation interventions; and academic training focused on home environment support and organizational skills. Half of the participants

will also receive medication decision-making interventions (MIP): ADHD medication psychoeducation, family decision-making interventions, and (for those who elect to start medication) coordinated medication management. Half of the sample will have comorbid substance use problems. Treatment will occur in three community clinics; therapists will be randomly assigned to study condition. Caregivers and adolescents will complete assessments at baseline, 3, 6, and 12-month follow-up. Multilevel modeling will compare the effectiveness of each condition on key patient and service use outcomes. Patient-centered analyses will explore differential treatment effects based on (a) Medication decision (yes/no); (b) Substance use comorbidity (yes/no); (c) Race/Ethnicity (Hispanic, African American).

Quantitative outcome analyses will test for service use effects, symptom reduction, and quality of life improvements that are primary reasons for seeking clinical services. Qualitative interviews will document family-specific rationale for decisions about medication, compliance with behavioral and medication interventions, and suggestions for improving services and service integration. Note that families assigned to CASH-AA Only will retain the option of pursuing ADHD medication through treatment-as-usual procedures at their respective clinic. Similarly, families assigned to CASH-AA + MIP will not be required to start ADHD medication. Instead, they will receive informed-choice interventions and can choose when and if to start medication; the study will assess the impact of these decisions on clinical outcomes.

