Hypothesis 3: Better Treatment Attendance. Integrated clients will attend more behavioral therapy sessions and medication management sessions than Behavioral Only clients.

Hypothesis 4: Greater Medication Acceptance and Treatment Satisfaction. Integrated clients will more often consent to medication, show greater medication compliance, and report greater overall satisfaction than Behavioral Only.

Aim 3: Examine Patient-Centered Outcomes

Research Question 1: Heterogeneity of Treatment Effects. Will clients with co-occurring substance use problems have worse treatment outcomes than those without? Will there be outcome differences based on age, ethnicity, sex?

Research Question 2: Analysis of Individual Differences. Across treatment conditions, will clients who choose to start a medication regimen have better treatment outcomes than those who do not?

Study Design

This study emphasizes ecological validity: Both protocols will be implemented in existing outpatient behavioral services by agency clinicians. To promote internal validity, randomization will occur within site at both the client and therapist level (i.e., study therapists at

each site will be randomly assigned to condition). The primary benefit of “doubly randomized” designs is that they minimize potential bias related to site effects—because randomization occurs within each site—and therapist sampling bias—because therapists are randomly assigned to condition. The use of a Behavioral Only condition will control treatment expectancy effects. Therapists will be trained and supervised to implement CASH-AA and MIP as part of their otherwise routine duties; that is, the protocols will be additional components of their usual practice for study cases. To maximize protocol exposure, and to promote consistency in the timing of protocol implementation across conditions and cases, therapists will be asked to implement CASH-AA and MIP at the start of treatment (unless contraindicated).

Note: (1) ADHD medication will be available to all Behavioral Only cases via routine site practices for ADHD treatment; and (2) MIP supports family decision-making about medication but does not require families to start a medication regimen.

Sample Description

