intensive family engagement and family-agency coordination efforts to help families overcome barriers to enrolling in services, procedures especially valuable for enrolling hard-to-engage families. Linking procedures will cease upon completion of the first intake interview (after which randomization will occur). After linking is completed, research staff will maintain contact with families solely to complete follow-up interviews, which will occur with every randomized family regardless of treatment attendance.

Randomization to study condition and therapist assignment. Cases will be randomly assigned to study condition after completing an intake interview at the assigned site. Urn randomization will promote balance between conditions on 3 variables: sex, ethnicity (Hispanic, African-American, Other), and ASU problems (Yes, No). Once randomized, cases will be assigned to a study therapist in alternate turns. Note that in some sites, it will be necessary to follow “nearly random” assignment to condition, if the given site assigns cases to clinicians based on a shared rotation of case assignment. That is: Any given case is assigned to the next available clinician in the duty rotation, or, the clinician who is on duty during the given intake appointment. Treatment site therapists who agree to participate as study therapists will be consented in their private offices by research staff. We anticipate some degree of therapist dropout due to staff turnover during two years of enrolling study cases. When a study therapist drops out in either condition, the given site will be asked to nominate two potential replacements, and the new therapist will be randomly selected from that pair. All partnering treatment sites will be in close proximity to assigned study participants and easily accessible via public transportation. Each site will routinely prescribe weekly treatment sessions and offer in-house psychiatric support for all cases. All therapists at each site who treat adolescent clients and who volunteer to participate will be accepted into the study randomization pool.

Study Conditions

Behavioral Only Condition: Changing Academic Support in the Home for Adolescents with ADHD (CASH-AA)

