As occurred during the pilot tests of the MIP and CASH-AA protocols, the proposed study will provide on-site training in CASH-AA (3 hours) to all study therapists, led by study investigators. Study investigators will then continue training therapists in the Integrated condition in MIP (additional 3 hours). After initial training, two separate monthly fidelity monitoring meetings will occur at each site, one for each study condition. Ad hoc training will be provided to new therapists whenever there is staff turnover.

Fidelity monitoring (FM) meetings will be organized using principles of localized quality assurance procedures for promoting the sustainability of evidence-based practices in usual care. Specifically, FM meetings will feature data from the therapist-report CASH-AA and MIP fidelity measures, along with a therapist-report measure of evidence-based practices for adolescent

conduct and substance use problems, as quality assurance tools and clinical supervision aids. Also, over the course of the study FM meetings will follow a multistep process to develop on-site clinical expertise and incrementally increase on-site supervision responsibilities in proportion to decreased extramural involvement.

Study Measures

Client Demographics, Multidomain Risk Factors, and Psychiatric Diagnoses

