The *Comprehensive Addiction Severity Index for Adolescents (CASI-A)* collects demographic information on high-risk adolescents and their families and also assesses risk factors in education (academics, attendance, behavior, attitudes), family relations (history of drug use/criminality, abuse/neglect), and legal involvement (illegal activities, involvement in juvenile justice). The CASI-A has demonstrated strong reliability and validity with clinical chart reviews of adolescents receiving inpatient psychiatric or substance use treatment and with diagnostic interviews such as the CIDI and DISC. The *Mini International Neuropsychiatric Interview (MINI)* (Version 5.0) is a brief structured diagnostic interview that assesses DSM diagnoses in adolescent and adult populations: ADHD, ODD, CD, SUD, GAD, PTSD, MDD, and Dysthymia. It has demonstrated interrater and test-retest reliability on international samples of psychiatric and non-psychiatric patients, has shown excellent convergent validity with the SCID and the CIDI, and is designed to be administered to treatment-seeking clients by lay interviewers. As in previous studies, the 18 ADHD diagnostic items on the MINI will also be administered at each FU interview to provide a dimensional assessment of ADHD symptoms.

Adolescent Behavioral Symptoms

The *Child Behavior Checklist (CBCL)* is a parent self-report measure that assesses children's externalizing and internalizing symptoms. It has demonstrated strong reliability, criterion validity, and convergent validity with other established measures of child psychological symptoms. The *Youth Self-Report* is a youth-report version of the CBCL with equivalent items, dimensions, and psychometric properties. The *Self-Report Delinquency Scale* assesses adolescent criminal behavior and peer criminal behavior; it is well-validated and has been used extensively with African American and Hispanic populations. The *Timeline Follow-Back method (TLFB)* measures quantity and frequency of daily consumption of substances using a

calendar and other memory aids to gather retrospective estimates. It is frequently used to assess substance use in treatment-referred, ethnic minority adolescents.

Quality of Life Indicators

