Study therapists will be asked to provide four kinds of study data: (1) Upon consenting to participate in the study, therapists will complete one questionnaire documenting their demographic characteristics and clinical training background, and a second questionnaire documenting their clinical strengths and preferred clinical practices. (2) When treating study cases, therapists will complete and submit the CASH-AA fidelity checklist and, for those in the Integrated condition, the MIP fidelity checklist after every session; and each condition will complete a brief checklist of evidence-based practices for adolescent behavior problems; all checklists (total completion time: 5 minutes) will be collected by research staff on a regular basis. (3) When treating study cases, therapists will audiorecord every session with consenting clients and submit the recordings to research staff on a regular basis. (4) Upon closing a study case, therapists will complete a termination summary of clinical activity that documents information about sessions held, participants in sessions, and treatment procedures that were the main foci of session activity.

Data Analysis

Preliminary Analyses and Refuser Analyses

All analyses will be preceded by examining distributional properties of variables, outliers, and need for using transformed variables or non-parametric tests. We will examine whether randomization successfully created equivalent study groups by conducting *t*-tests or chi-square tests on demographics and other variables; those that differ between groups will be entered as covariates in subsequent analyses. Logistic regression will examine potential biases due to failure to contact clients at follow-up on baseline characteristics, study condition, and their interactions. These analyses will determine whether the followed sample differs from the randomized sample and whether there is differential attrition by condition. Also, analyses on refuser characteristics will be conducted to inform the generalizability of the sample, as follows. Families completing the phone eligibility screening instrument will provide information on personal and family demographics. Families of eligible adolescents who refuse to participate in the baseline interview, or who participate in the baseline interview but do not complete an intake appointment at the assigned treatment site, will be asked to complete a brief study refuser

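### The Behavioral Only arm controls the general expectancy of being in a study protocol but not expectancy specific to MIP, and no masking of follow-up interviewers is stated

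*Combined protocol and SAP*

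**What the plan says.** The Study Design section of the combined protocol and SAP states, without qualification or mechanism, "The use of a Behavioral Only condition will control treatment expectancy effects".

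The arms are described in the Project Abstract: "This parametric comparative trial will randomly assign 140 inner-city adolescents with ADHD to (1) CASH-AA Only or (2) CASH-AA + MIP". On the shared component it says "All participants will receive behavioral interventions (CASH-AA"), and on the added one that half of the participants "will also receive medication decision-making interventions (MIP"). Under Therapist Training and Fidelity Monitoring Procedures, all study therapists are trained in CASH-AA, and then "Study investigators will then continue training therapists in the Integrated condition in MIP (additional 3 hours").

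On measurement, Study Measures says that "the 18 ADHD diagnostic items on the MINI will also be administered at each FU interview", which supplies the dimensional ADHD outcome. On staff roles, the paragraph on linking to treatment says that after linking, "research staff will maintain contact with families solely to complete follow-up interviews". Procedures For Obtaining Informed Consent confirms that research staff conduct the 3-, 6- and 12-month interviews. Therapist Measures says that the session checklists, including the MIP checklist that only Integrated therapists complete, "will be collected by research staff on a regular basis"; session recordings go to research staff as well.

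**The concern.** An active comparator controls expectancy only for what the two arms share. Here they share CASH-AA and routine clinic services. The tested contrast is MIP: a psychiatric consult, education about the benefits and course of medication, family decision sessions and, for those who choose it, coordinated medication. Behavioral Only contains nothing matched to this, and no section describes a measure of expectancy. Families experience the content of their treatment openly, and most Aim 1 outcomes are their own ratings.

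The interviewers are a second route for bias. The MINI is described as a structured interview suited to lay interviewers. If an interviewer knows the condition, that knowledge can colour how symptom items are probed and scored. The plan states no safeguard against this.

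At stake is how an Aim 1 difference is read. Taken at its word, the Study Design sentence lets a reader treat a difference in rated symptoms as the effect of integrating medication decision-making with expectancy already removed. The design cannot show that.

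**Working it through.** **No figure to reproduce.** The documents give a sample of 140 but no significance level, power, effect size or SD. The check is therefore a comparison of sections, followed by an illustration.

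**1. What the comparator shares with Integrated** (Project Abstract; Study Conditions)

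| Element | Behavioral Only | Integrated |
|---|---|---|
| Routine clinic services | yes | yes |
| CASH-AA, with training and fidelity monitoring | yes | yes |
| MIP | no | yes |
| ADHD medication | possible through site routine | possible, supported by MIP |

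The first two rows are controlled. The MIP row is not.

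**2. Who supplies the Aim 1 outcomes** (Study Measures). Family-informed: MINI ADHD items, CBCL, Youth Self-Report, delinquency scale, TLFB, BRIEF, CASI-A and Bonding to School. Record-based: school transcripts. That is 8 of 9 sources from families.

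**3. Which outcomes an interviewer can influence.** The section on baseline interviews lists two modes, structured clinical interviews and audio computer-assisted self-report. It does not say which instrument uses which. The MINI is an interview by its own description, so interviewer bias matters mainly there and for any other measure given by interview.

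**4. Masking and roles.** No section masks families, therapists, interviewers or analysts. Research staff conduct follow-ups, and research staff collect the MIP checklists and the recordings. Fidelity meetings are held separately for each condition, and research team members take part (Potential Risks for Therapist Participants). The rule that contact after linking is limited to interviews restricts contact with families, not what interviewers may see. The confidentiality rule keeping research data from the clinics protects the other direction.

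**5. What families are told** (Procedures For Obtaining Informed Consent). The script describes a lottery between therapists who use research tools to educate clients and therapists who use their regular procedures. It names neither MIP nor medication. It also fits poorly with the Project Abstract and Study Conditions, where therapists in both arms deliver CASH-AA.

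**6. Illustration of size.** Assumptions: 1:1 allocation, so 140 / 2 = 70 per arm; one standardized outcome; two-sided 5% level; no clustering; true effect zero; reporting shift b in SD units. The values of b are assumed, not taken from the documents.

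SE = sqrt(2/70) = 0.169

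P(significant) = Φ(b/SE − 1.96) + Φ(−b/SE − 1.96)

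| b (SD) | b/SE | 70 per arm | 59.5 per arm |
|---|---|---|---|
| 0 | 0 | 5.0% | 5.0% |
| 0.1 | 0.59 | 9.1% | 8.5% |
| 0.2 | 1.18 | 21.9% | 19.4% |
| 0.3 | 1.77 | 42.7% | 37.3% |

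The last column uses 15% missing data, the upper end of the range in Analytic Plans for Missing Data: 70 × 0.85 = 59.5. Therapist clustering would lower the figures further. With 15% missing and an assumed design effect of 1.5, significant results in the direction of the shift alone occur in 6.5%, 14.2% and 26.6%, against a nominal 2.5%.

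The formula is symmetric in b. A shift against Integrated of the same size gives the same rates with the sign reversed, and it can also hide a benefit. If a true benefit of 0.3 SD met a shift of 0.2 SD the other way, the net difference would be 0.3 − 0.2 = 0.1 SD, and the chance of significance at 70 per arm would fall from 42.7% to 9.1%.

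**The case against.** The strongest defence is that an open comparison is legitimate in an effectiveness trial that puts ecological validity first, and that added contact is part of what integrated care is. Hypothesis 3 itself predicts more sessions in the Integrated arm. This stands: nothing here asks for blinded families or an attention-matched comparator. It does not rescue a sentence that claims control of expectancy.

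Other parts of the defence limit what can be said:

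- **The sentence is not baseless.** Both arms receive an active, trained and monitored protocol, which does control the general expectancy of receiving a study treatment.
- **Families may not know the contrast.** They know what treatment they receive, but the consent script does not tell them what distinguishes the arms. A reader might infer that they know which arm is expected to do better; the documents do not show it.
- **The direction is open.** A reader might assume bias toward the arm with more treatment. Study Purpose And Aims says that families in these settings prefer behavioral services only, and the Project Abstract mentions stigma around medication.
- **Medication use does not identify the arm.** Behavioral Only families may obtain medication and Integrated families may decline it. The timing of the SACA and of the satisfaction questionnaire is also not given. Item order is a sensible precaution, not the cure of a proven unmasking.
- **Computer-assisted self-report** limits interviewer influence on the measures that use it, and masking interviewers does nothing for bias in the families' own ratings.

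**Conclusion.** The point holds in limited form. The expectancy sentence is too broad: it is right for general expectancy and wrong for expectancy specific to MIP, which is the contrast that Aim 1 tests. The absence of interviewer masking and of a stated role split is an omission. A reader might infer that the same people handle MIP checklists and interview families; the documents use one label for both tasks but do not say so.

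The figure of about 9% to 43% rests on assumed shifts of 0.1 to 0.3 SD, 70 per arm, no clustering and a simple two-group comparison instead of the planned growth model. It shows that a modest bias would matter in a trial of this size. It does not estimate the bias in this trial.

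School transcripts may look like an objective check on the ratings. They are not a sound one. Therapists who know the condition acquire them, and Study Purpose And Aims itself doubts that long-term medication alone improves academic functioning. Transcripts could therefore disagree with a real symptom effect, and conclusions should not be made to depend on their agreement.

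**What to change.** 1. Replace the Study Design sentence with: *Behavioral Only controls for CASH-AA, usual services and the general expectancy of receiving a study protocol; it does not control for expectancy specific to MIP, and Aim 1 differences on reported outcomes may include it.*
2. State that, within existing research staff, those who collect therapist checklists or recordings or attend fidelity meetings do not conduct follow-up interviews, and that interviewers are not told the condition.
3. Fix the interview order so that the MINI ADHD items come before any question on medication or service use, including the 12-month qualitative interview on medication decisions.
4. Reconcile the consent script's description of the two groups with the Project Abstract and Study Conditions, where both arms receive CASH-AA.

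This costs protocol and consent wording, slightly less flexible staff scheduling and a more modest claim. It needs no additional participants or instruments. Bias in caregiver and adolescent ratings will remain, which is why the first change is needed as well as the second and third.

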Baseline Eligibility Interviews and Consent into the Follow-Up Study. Baseline research interviews will be conducted primarily in the home or in the partnering clinic site, but also in other locations upon request. Caregivers and adolescents will be consented and interviewed separately; caregivers will consent for themselves and their teens, and teens will assent for themselves. Assessment measures will consist of structured clinical interviews and audio computer-assisted self-report measures. Caregiver assessments will be administered in English or Spanish as preferred. Each member will receive a \$40 honorarium in store vouchers for completing the interview (60-75 minutes). After members complete the baseline interview, staff will confer regarding eligibility for the follow-up study. Eligible families will then be consented to participate in the follow-up study (caregivers and adolescents will again consent separately), which includes assisted enrollment in a partnering treatment site in which site clinicians have been trained in the study protocols (MIP, CASH-AA). Following this final consenting process, staff will meet with both family members to answer any questions, and for consenting families, prepare the family for linking to treatment (described below). Families will then be scheduled for follow-up interviews to be conducted 3, 6, and 12 months from the date of the baseline; each member will receive a \$50 honorarium in store vouchers for completing the 3- and 6-month interview (60 minutes apiece), and \$100 in certificates for the 12-month interview (75 minutes). Non-eligible and non-consenting families will be offered a referral to appropriate behavioral services as requested.

Linking to treatment. The goal of treatment linking is to ensure that families enrolled in the study complete an intake appointment at the designated treatment site. Families drawn from community referral partners will be assigned to a designated site based on site capacity and geographical proximity; families drawn from the referral stream of a partnering site will continue in that site's enrollment process. Once assigned to a designated site, research staff will use

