Client research interviews (phone screen, baseline interview, and 3-, 6- and 12-month follow-up interviews) will be conducted by research staff primarily in the home or site clinical offices but also in other locations upon request. Caregivers and teens will be consented and interviewed separately; caregivers will consent for themselves and for their adolescents, and adolescents will assent for themselves. Recruitment procedures, randomization procedures, and assessment measures and procedures are fully described above. Caregiver consents and assessments will be administered in the preferred language: English or Spanish. Many assessment measures have Spanish versions available from the vendor; all other measures, and all consents, will be translated by a professional translation agency using back-translation techniques that are high-standard methods in the field. Clients will be fully informed about the general treatment services to be offered—with at least some focus on attention and impulsivity problems—and about randomization procedures prior to consenting to participate, in the following manner: “You and your teen agree to enter a lottery at the counseling program. Half of families in the study will be assigned to therapists who will use research tools to educate their clients about attention problems in adolescents, and half will be assigned to therapists who will use their regular procedures to educate clients. All study families will receive the same access to

all available services at the clinic.” Research staff will give a copy of the consent/assent form (consent/assent to participate in the study; consent/assent to audiotape sessions) to caregivers and adolescents, read them aloud, and then ask family members if they have any questions, clarifications, or concerns before signing. After consenting/assenting to study participation and completing the Baseline interview, families will then be linked to services at a partnering treatment site by research staff using intensive family-based engagement strategies (also described above). Caregivers will receive \$25 in vouchers for completing the Phone Screen, and caregivers and adolescents will each receive \$40 for completing the Baseline interview, \$50 apiece for the first two follow-ups, and \$100 apiece for the final follow-up interview

Site Therapists

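### Client and therapist randomisation is stated without exception, but at some sites the duty roster sets a client's condition, and no draw of condition is described for replacement therapists

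*Combined protocol and SAP*

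**What the plan says.** **The claim.** Study Design states that "randomization will occur within site at both the client and therapist level". It credits such designs with reducing two biases: "they minimize potential bias related to site effects", and they guard against therapist sampling bias because therapists too are randomised to condition. The consent script under Procedures For Obtaining Informed Consent tells caregivers: "You and your teen agree to enter a lottery at the counseling program".

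**The default for clients.** Under Randomization to study condition and therapist assignment: "Cases will be randomly assigned to study condition after completing an intake interview at the assigned site". Then: "Urn randomization will promote balance between conditions on 3 variables", namely sex, ethnicity and adolescent substance use problems. Cases then go to study therapists in alternate turns.

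**The exception for clients.** The same paragraph says that some sites must use an assignment to condition that it describes as only close to random, because they share cases by rotation. There a case is "assigned to the next available clinician in the duty rotation, or, the clinician who is on duty during the given intake appointment".

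**Therapists.** Volunteers enter a randomisation pool. Turnover is expected over two years of enrolment. When a therapist leaves either condition, "the given site will be asked to nominate two potential replacements, and the new therapist will be randomly selected from that pair".

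**What already protects the comparison.**
- Consent and baseline precede intake: "Eligible families will then be consented to participate in the follow-up study" and only then linked to a site.
- Families who do not complete intake are asked for a refuser measure.
- Groups are tested for baseline equivalence, and variables that differ become covariates.
- Site, sex and ethnicity are fixed covariates in all outcome models.
- Baseline substance use is a predictor in the Aim 1 and 3 models.

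**The concern.** Study Design rests its low-bias argument on randomisation of both clients and therapists. Where the roster decides who treats a client, it also decides the client's arm, and that is not a random draw. A roster can be known in advance, and no concealment step is described for those sites. Bias would be possible if intake staff could foresee the on-duty clinician, or if families completed intake more often with some clinicians than with others.

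For therapists, drawing one of two nominees randomises the person and not the condition. The natural reading is that the replacement fills the vacant condition, and the site, which forms the pair, may know which one that is.

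At stake is how far a causal claim can be carried over the whole sample. The plan provides no list of rotation sites, no record of allocation method for each case and no report split by method, so a reader of the results could not judge this.

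**Working it through.** The plan gives no figure to reproduce here. The main check is textual; the arithmetic shows scale.

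**1. Client allocation.** Study Design allows no exception; the randomization paragraph does. Therapists belong to one condition, so assignment to a clinician is assignment to an arm. That no urn runs at rotation sites is an inference: the text describes no urn step there, and the roster leaves no room for one.

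**2. Timing.** The default puts assignment after intake. The exception has two variants. Under the next-available-clinician variant, assignment can still follow intake. Under the on-duty variant, condition in effect follows from who is on duty during intake. Only that variant conflicts with the stated order.

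**3. Therapists.** Original therapists are randomised to condition. For replacements, a random choice of person is described and a draw of condition is not. At urn sites the client's condition is still drawn individually before a therapist is assigned, so client randomisation there is unaffected.

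**4. Share of clients.** N = 140. The Project Abstract has three clinics; Study Purpose And Aims and the nesting section have four. Assume equal enrolment.
- Four sites: 140 × 1/4, 2/4, 3/4 = 35, 70, 105 for one, two or three rotation sites.
- Three sites: 140 × 1/3, 2/3 = 47, 93 for one or two.

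**5. Substance use (SU) in Aim 2.** The Aim 2 models take the nuisance covariates listed for Aims 1 and 3 (sex, age, ethnicity, income, caregiver education, site). SU is not among them, so it enters Aim 2 only if the baseline test finds a difference. Assumptions: urn sites balanced, equal arms within rotation sites, independent clients, roster unrelated to SU, and prevalence p from 20% to 50% (the Sample Description range; the Project Abstract says half).

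Chance gap in SU between arms over the whole trial: SD = (n/140) × √(4p(1−p)/n), with n roster clients.

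| n | p = 0.5 | p = 0.2 |
|---|---|---|
| 35 | 4.2 points | 3.4 points |
| 70 | 6.0 points | 4.8 points |
| 105 | 7.3 points | 5.9 points |

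The plan gives no threshold for the baseline test; assume 0.05 with an uncorrected chi-square and 70 per arm. The smallest significant splits are then 41 v 29 at p = 0.5 (12/70 = 17.1 points, P = 0.043) and 19 v 9 at p = 0.2 (10/70 = 14.3 points, P = 0.035). In simulation, chance produces a significant test in under 3% of trials in every case above.

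With an assumed SU effect of 0.2 to 0.5 SD on the outcome, a 1-SD chance gap shifts an Aim 2 estimate by 0.034 × 0.2 = 0.007 SD up to 0.073 × 0.5 = 0.037 SD.

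**6. What added reporting could show.** Outcomes are in SD units, clients are taken as independent and arms as equal.
- Baseline difference within rotation sites: SE = 2/√n = 0.338, 0.239, 0.195 for n = 35, 70, 105. The 95% half-widths (× 1.96) are 0.66, 0.47, 0.38 SD.
- Shift of an urn-only estimate from the full-sample estimate: SE = √(4/n_urn − 4/140) = 0.098, 0.169, 0.293 for 105, 70, 35 urn clients. The half-widths are 0.19, 0.33, 0.57 SD.

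The second line is for a simple mean difference, not the planned growth-curve slope. Clustering by therapist would usually widen both.

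**The case against.** The strongest reply is that nothing is hidden. The randomization paragraph names the exception, says when it applies and how it works, so only someone who reads Study Design alone would be misled. That stands: this is an inconsistency between sections, not a concealed departure.

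A second reply is that a rule followed by its stated exception is not a contradiction in timing. That stands for the next-available variant and fails for the on-duty variant.

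Third, filling a vacant slot in an originally randomised condition is ordinary practice. A reader might infer that clients of replacement therapists are not randomised. The documents do not support that: at urn sites these clients are still randomised individually. What is weakened is the protection against differences between therapists.

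Fourth, much is already adjusted for. Sex and ethnicity are covariates in every model, and SU is in the Aim 1 and 3 models, so lost urn balance is covered on all three variables for those aims and on two of three for Aim 2. That also stands, but adjustment for measured variables does not make roster allocation random. Site as a fixed effect removes differences between sites, not selection within a site. The planned within-site re-analysis is triggered by a significant site effect, not by allocation method.

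Finally, the SU point would exist even if every site used the urn, and it is small. It is therefore kept apart below.

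**Conclusion.** The statement that clients and therapists are both randomised is wrong as written, in a limited way. Clients at rotation sites are quasi-randomised, and replacement therapists are not described as randomised to condition. Original therapists, and clients at urn sites, are randomised as claimed.

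A reader might go further and conclude that the comparison is biased. The documents do not show this: they do not show that rosters are foreseeable in practice or that intake completion differs by clinician. The number of rotation sites is not given, so the affected share is unknown; 35 to 105 of 140 is an illustration under four equal sites.

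The SU gap in Aim 2 is worth about 0.01 to 0.04 SD for a 1-SD chance imbalance, under the assumptions stated with the calculation. That is a small gain at almost no cost, not a threat to the results. The change is worth making because it is cheap and because allocation method is best recorded as cases enrol.

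**What to change.** 1. **Wording.** Qualify Study Design and the consent script: clients at rotation sites are quasi-randomised, and replacement therapists are not described as randomised to condition. Limit the causal claim for roster-allocated clients only. Clarify when condition is set under the on-duty variant.
2. **Recording and reporting.** Name the rotation sites. For each case, record the allocation method and whether the therapist is original or a replacement. Report baseline balance by condition within rotation sites as standardised differences with confidence intervals, noting that only large imbalances would show. Any urn-only estimate is descriptive: it is confounded with site and too imprecise to confirm or rule out a plausible bias.
3. **Optional.** At rotation sites able to hand cases over, use the roster for intake and apply the urn assignment afterwards. Some sites may be unable to do this.
4. **Separate improvement.** Make baseline SU, already collected, a fixed covariate in the Aim 2 models instead of leaving it to a baseline significance test.

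Cost: one or two data fields per case, one table, one covariate and no extra participants, plus some hand-overs if item 3 is adopted. The design will also read less favourably than it does now.
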